5.1 Description

The study drug, rhDNase I, will be supplied as a 1 mg/ml (0.1%) solution for administration as topical eye drops. The control group will receive Vehicle eye drops as placebo. Vehicle (placebo) contains all ingredients as Pulmozyme with the exception of the active ingredient (dornase alpha), and is dispensed in identical single-use ampules.

Each subject will receive either 0.1% rhDNase I (study drug) or Vehicle(placebo) solution, as a single eye drop in each eye four times a day (QID) for eight weeks. Except for the first dose on Day1, subjects will self-administer the test medication eye drops at home.

Subjects will not be charged for the test medication in any way (neither the cost of the medication nor its dispensing cost).

5.2 Treatment Regimen

Study drug group- rhDNase I, 1mg/ml (0.1%) eye drops will be applied to both eyes q.i.d for 8 weeks. Control group – Vehicle eye drops will be applied to both eyes q.i.d for 8 weeks. For either group, the subject will be instructed to instill the first dose of the study medication in the morning at approximately 8 a.m., and then the remaining doses at approximately 4 hourly intervals. Therefore, doses will be scheduled at approximately 8 a.m., 12 noon, 4 p.m. and 8 p.m.

5.3 Method for Assigning Subjects to Treatment Groups

This Randomized placebo-controlled trial will have two study groups. Subjects will be randomly assigned to one of two groups (#1, #2). One group will receive the study drug (rhDNase 0.1%; test group), and the other group will receive placebo (Vehicle; control group). We will use a computer-based random code generator (Research Randomizer; http://randomizer.org/) to generate 1 set of 72 non-unique, unsorted numbers with a range from 1 to 2 representing the group number (#1/ #2). Each subject will be assigned a study identification (ID) number at screening, eg. subject #1, subject #2, subject #3 and so on. Based on the randomizer generated table, subject #1 will receive either placebo or study drug. This will be repeated for each subject. For reproducibility purpose, we will document the final randomization schedule and the random SEED number used to generate the schedule. Randomization will be performed by the Illinois Eye and Ear Infirmary's pharmacy, and neither participants nor research staff will be aware of the assigned treatments. The person conducting the randomization will remain masked as well.

The study identification (ID) number will be used on all study-related documents. To maintain confidentiality, the subject's name will not be recorded on any study document other than the informed consent form. The drug vial number will be linked to the subject identification number.

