6.2 Assignment of Subject Identification

A study identification (ID) number will be assigned to each subject at screening. This study ID number will be used on all study-related documents. To maintain confidentiality, the subject's name will not be recorded on any study document other than the informed consent form. The master code list will link the subject MRN to the study ID number given to each subject. The master code list will be stored on the desktop in PI's OFFICE in Lions of Illinois Eye Research Institute (LIERI). The data collected and master code list will be accessible only to the PI and the research team involved in this project. The desktops will be password protected as well. Data will not be shared over the internet and will remain password protected. Confidentiality will be maintained. Data will be de-identified once study is completed and for subjects determined to not meet eligibility criteria or who later decline participation in the consent process.

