6.3 Screen Failure

A record of screen failures and the reasons for non-eligibility to the study will be maintained.

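### As written, the 72 unrestricted draws keyed to the screening ID do not deliver the stated 72 subjects at 36 per group (minor)

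*Combined protocol and SAP*

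**What the plan says.** The Study Summary and Section 3.1 give 72 subjects, 36 per group. Section 7.1 requires 30 per group and elects to enrol 36.

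Section 5.3 uses a computer randomiser "to generate 1 set of 72 non-unique, unsorted numbers with a range from 1 to 2 representing the group number". No blocking, stratification or balance constraint is stated. The list is read by subject number: "Based on the randomizer generated table, subject #1 will receive either placebo or study drug", and so on for each subject. That number is given before eligibility is known: "Each subject will be assigned a study identification (ID) number at screening". Section 6.2 confirms the timing.

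The screening ID is the only subject number that the plan defines. Section 5.3 says "The drug vial number will be linked to the subject identification number", and Section 6.2 says "The master code list will link the subject MRN to the study ID number given to each subject".

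The plan expects some ID holders never to be randomised. Section 6.2 covers de-identification of data "for subjects determined to not meet eligibility criteria or who later decline participation in the consent process", and Section 6.3 states "A record of screen failures and the reasons for non-eligibility to the study will be maintained". Section 8.1 also allows subjects who withdraw because of an adverse event to be replaced. Section 6.5.2 places randomisation at Visit 2 (Day 1), by the pharmacy, without saying which number is used.

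**The concern.** A stated procedure and a stated size do not match, in two ways.

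- **Balance.** Independent draws of 1 or 2 produce 36 per group only on average, yet the figure is given without qualification in three places.
- **Index.** A list of exactly 72 lines, read by an ID that screen failures also receive, covers 72 randomised subjects only if nobody fails screening and nobody is replaced. The plan does not say whether a screen failure's line is skipped or passed on, which line a replacement takes, or how the list is extended.

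At stake is whether the person allocating treatment follows a rule fixed in advance or has to supply one during the trial.

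**Working it through.** **Inputs.** Section 7.1: control mean 3.1, treated mean 1.24, SD 2.5, two-sided alpha 0.05, 80% power, two-sample t test. Section 5.3: 72 draws from {1, 2} with repeats allowed. The screen-failure rate is not given.

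**1. The plan's own sample size.** The difference is 3.1 − 1.24 = 1.86. The normal approximation gives 2 × [2.5 × (1.960 + 0.842) / 1.86]² = 28.4, so 29 per group. Exact power uses the noncentral t distribution with n₁ + n₂ − 2 degrees of freedom and noncentrality 1.86 / [2.5 × √(1/n₁ + 1/n₂)]. It is 0.795 at 29 per group and 0.809 at 30. The stated 30 reproduces. At the planned 36/36, power is 0.876.

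**2. Arm sizes under Section 5.3.** Let X be the size of one arm, X ~ Binomial(72, 0.5), with SD √(72 × 0.25) = 4.24.

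| Quantity | Result |
|---|---|
| P(X = 36) | 0.094 |
| 2.5th and 97.5th percentiles | 28 and 44 |
| P(28 ≤ X ≤ 44) | 0.956 |
| P(smaller arm below 30) = 2 × P(X ≤ 29) | 0.125 |

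**3. Cost in power, total fixed at 72.**

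| Split | Power |
|---|---|
| 36/36 | 0.876 |
| 30/42 | 0.866 |
| 29/43 | 0.863 |
| 28/44 | 0.859 |
| Average over the binomial distribution of splits | 0.871 |

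The average loss is 0.876 − 0.871 = 0.005. An arm below 30 does not bring power below 80%, because the other arm is correspondingly larger.

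**4. The index: two readings.**

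- *Line = screening ID* (the literal text). If k of the first 72 IDs are never randomised, the list allocates 72 − k subjects. Allocating 72 takes about 72 / (1 − f) lines on average. At assumed screen-failure rates f of 5%, 10% and 20%, that is 76, 80 and 90.
- *Next unused line at Day 1.* Seventy-two lines cover 72 randomised subjects, plus one more line for each replacement.

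The readings part at the first screen failure. Suppose ID 5 fails: ID 6 takes line 6 under the first reading and line 5 under the second. Two independent draws differ with probability 2 × 0.5 × 0.5 = 0.5. The readings can also part with no failures at all, because Section 6.5.1 sets different intervals to Visit 2 for subjects with and without a washout, so subjects may reach Day 1 out of ID order.

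**The case against.** The best defence is that randomisation takes place on Day 1, in the pharmacy, after screening. A screen failure never reaches that step. Seventy-two lines for 72 subjects suggest that one line per randomised subject was meant. Unrestricted randomisation is a valid method, and 36 per group can be read as a target. Much of this stands: that is the likely intent, and the effect is small. But Section 5.3 ties the line to the number given at screening, no other number is defined, and 36 is stated as a fact of the design.

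Two stronger readings are tempting, and the documents support neither.

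- A reader might infer that the 72-line list caps enrolment, so that screen failures erode power. Nothing makes list length a limit on enrolment, and adding further independent draws introduces no bias.
- A reader might infer that allocation could not be reconstructed afterwards. Section 5.3 commits: "For reproducibility purpose, we will document the final randomization schedule and the random SEED number used to generate the schedule". It also links vials to IDs, and Section 6.3 keeps a record of screen failures. The accurate statement is that the rule is not specified in advance.

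**Conclusion.** The point holds and is minor. As written, the method does not deliver 72 subjects at 36 per group. Exact balance has probability 9.4%, an arm falls below 30 with probability 12.5%, and the list runs short after any screen failure or replacement if it is keyed to the screening ID.

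There is no bias. Mean power is 0.871 rather than 0.876, and there is no further loss if the list is extended. The sample-size calculation itself is sound on its own inputs.

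The balance probabilities need only fair, independent draws. The power figures rest on the Section 7.1 inputs, which concern an RBS score and a t test. Section 3.2 now names fluorescein and lissamine staining and Section 7.2 plans a mixed model, so those figures are indicative. The screen-failure rates are assumptions and only illustrate the shortfall.

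**What to change.** Amend Sections 5.3 and 6.2 to state:

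- Once eligibility is confirmed on Day 1, the pharmacy assigns the next unused randomisation number in sequence. That number sets the group and is linked to the study ID and the vial number.
- Screen failures use no randomisation number.
- A replacement takes the next unused number, and the subject replaced keeps the allocation already made.

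Then choose one of the following:

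- **(a) Blocks.** Use a pharmacy-held schedule with concealed varying block sizes, 36 per arm for the first 72, and spare blocks from the documented seed for replacements. The downside is slight predictability in a single-centre trial.
- **(b) Unrestricted draws.** Keep them, generate further lines from the documented seed for replacements, and restate the size as *approximately 36 per group* in the Study Summary and Sections 3.1 and 7.1. This costs only a wording change.

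If enrolment has begun, apply the change only to subjects not yet randomised, leave existing allocations alone, and document the date and the list used. The overall cost is a short amendment, a longer pharmacy list and one extra linking number in drug accountability. No visits are added.

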5.4 Preparation and Administration of Study Drug

The study medications will be stored, packaged and dispensed from the UIC Eye and Ear Infirmary (EEI) Pharmacy. No modifications will be made to the study medication constituents. The drug will be re-packaged in sterile eye droppers for dispensing, as explained below:

The study medications will be dispensed in sterile eye droppers of 3 ml volume. The commercially available product is a single-use ampule containing 2.5 mL of study drug. The medication will be transferred to two sterile eye droppers of 3 ml volume. Approximately 1 ml of study drug will be transferred to each sterile eye dropper, thus 2 eye droppers (each containing 1 ml of the study medications) will be made from each commercially available ampule (containing 2.5 mL of study drug). This repackaging will be done at Illinois eye and ear infirmary (EEI) pharmacy, under standard aseptic precautions. The eye

droppers will be used by subjects as single-dose applications.

One drop of the drug/ placebo solution will be administered to each eye. Therefore 4 eyedroppers will be required per day. At each visits, subjects will receive 56 sterile multi-dose eye droppers that will be used as single-dose applications. Prepared eye droppers will be placed in a dark (brown) colored ziplock packet before being dispensed to the subject. The medications will need to be stored in a refrigerator (4 °C), away from direct strong light.

Instructions for Drug Use:

- 1. Wash your hands thoroughly with soap and water.
- 2. Check the dropper tip to make sure that it is not chipped or cracked.
- 3. Avoid touching the dropper tip against your eye or anything else eye drops and droppers must be kept clean.
- 4. While tilting your head back, pull down the lower lid of your eye with your index finger to form a pocket.
- 5. Hold the dropper (tip down) with the other hand, as close to the eye as possible without touching it.
- 6. While looking up, gently squeeze the dropper so that a single drop falls into the pocket made by the lower eyelid. Remove your index finger from the lower eyelid.
- 7. Close your eye for 2 to 3 minutes and tip your head down as though looking at the floor. Try not to blink or squeeze your eyelids.
- 8. Place a finger on the tear duct and apply gentle pressure.
- 9. If you are to use more than one drop in the same eye, wait at least 5 minutes before instilling the next drop.
- 10. Do not reuse the dropper after use. Use another dropper for next dose.

The subject should repeat the above procedures for the other eye to demonstrate to the Investigator or designee that they are able to perform the drug administration satisfactorily. Subjects will be instructed to perform these steps on each administration of the study medication. Instructions for use will be included in the zip-lock packet with the study medication and site personnel will ensure that these instructions are given to the subject.

5.5 Subject Compliance Monitoring

Subjects will receive their first dose of study medication on study Day 1 in the doctor's office and after completion of the study assessments will have the topical eye drops dispensed for self-administration.

Subjects will be provided with diaries to record the time of each dose and will also be asked to record any adverse symptoms. In addition, they will be asked to make a note of any missed doses together with the reason for the omission. Subjects will be asked to bring their diaries with them at the 2, 4, 6 and 8 week visits. Diaries will be reviewed with the subject by a member of the research team at each visit. Additionally, subjects will be asked to bring back the used and unused drug eye droppers at each study visit. Participants will be asked to return the unused eye droppers each study visit as a method to determine compliance.

5.6 Prior and Concomitant Therapy

Prior medications are defined as all medications taken within 30 days prior to Day 1, whether there is continued use or not. Concomitant medications must be identified in the subject's medical record, including all lubricants administered for oGVHD. These medications will be recorded in the case report form (CRF).

- For each medication taken, the following information will be collected:
- Medication trade name
- Eye that was treated, if applicable
- Indication for which the medication was given
- Date started
- Date stopped
- Dose of medication used.

In general, patients will be required to maintain the treatments that they were using at entry into the study throughout the follow-up period. Patients will be instructed to continue using the same brand of eye drops during the study as they were using at the screening visit. If patients are wearing contact lenses (Soft bandage contact lenses or PROSE lens), they will be asked to discontinue contact lense wear for 1 month prior to being enrolled (Baseline visit) and will be required to not wear contact lenses for the duration of the study (until week 10 visit). Patients will be enrolled if they have been using their eye treatments for at least 30 day prior to the baseline visit and patients will be asked to commit to continue using the same treatments for the duration of the study. Participants will be also be permitted to continue ancillary treatments such as eyelid massage or warm compresses of the eyelids. The number of drops and frequency must be recorded in the subject diary provided.

• The use of any investigational agent during past 30 days is prohibited.

There is currently no FDA approved treatment available to treat patients with oGVHD

Contact lenses, commonly used to treat oGVHD, will be withheld during the course of this study. This is necessary as the proposed primary efficacy outcome measure is corneal Fluorescein and Lissamine Dye Staining. Contact lenses can directly reduce corneal SPK and staining due to ensconcing and acting like a bandage that prevents corneal exposure to tear fluid inflammatory materials. Thus, because of over lapping effects on the primary outcome measure, it may not be possible to attribute any observed clinical benefit to rhDNase I treatment if contact lenses are used concurrently. This approach has been used in other clinical trials that have investigated the use of an anti-inflammatory agent in dry eye disease (NIH funded 'Dry Eye Evaluation and Management (DREAM) study').⁴¹

Stopping contact lens wear may increase the risk of worsening of oGVHD during the wash-out period and during the course of the study. However, because other eye drop treatments will continue during

the wash out period as well as during the course of the study, we do not expect any significant clinical worsening during the study. We do however expect the frequency of use of artificial tears to go up during the wash out period and during the course of the study.

The subjects will be monitored frequently (at 2 weekly intervals) to ensure that they are not subjected to any undue risks during the wash out period or during the course of the study. Additionally, they will be warned of the possible signs and symptoms of clinical worsening of oGVHD, and advised to contact the research team immediately in case any of those symptoms occur. Subjects will also be encouraged to contact the research team in case they experience any ocular discomfort during the wash out period or during the course of the study. The subject's condition will be monitored by the physician (Principal Investigator) at each study visit, as well as at any interim visit (in case of adverse symptoms, as mentioned above). Any worsening of oGVHD or any adverse event due to the study drug will be recorded. In case of clinical worsening, based on the individual subject's clinical condition, one or more of the following therapeutic decisions may be implemented: (1) Increasing the frequency of use of artificial tears, (2) Increasing the use of anti-inflammatory therapy (Restasis/ corticosteroids), (3) Withdrawal of the use of study drug (if worsening occurs during the course of the study). The decision will be made by the physician (Principal Investigator) based his clinical judgment as per the individual subject's clinical condition. If contact lens wear is instituted during the course of the study and/or the study drug is withdrawn, the subject will be withdrawn from the study. After any clinical worsening is noted, the subjects will be followed more closely (weekly) until complete resolution of symptoms and return to the subject's previous baseline.

5.7 Rescue Plan

The research staff, including the PI, will be masked to randomization, thus will not be aware if a particular subject receives study drug or placebo. Subjects will be monitored by the Principal Investigator at each study visit. Any worsening of oGVHD or any adverse event (AEs) will be recorded and in the case of AEs followed to resolution. In case of clinical worsening/ adverse event(s), based on the individual subject's clinical condition, one or more of the following therapeutic decisions may be implemented:

- (1) Increasing the frequency of artificial tears use,
- (2) Increasing the use of anti-inflammatory therapy (Restasis/ corticosteroids),
- (3) Discontinue the study drug.

The decision will be made by the Principal Investigator based on his clinical judgment and the individual subject's clinical condition. If contact lens wear is reinstituted and/or the study drug is discontinued, the subject will be withdrawn from the study. If an adverse event is severe enough to discontinue the subject from the study, the PI may decide to break the subject's randomization code if it seems relevant to the treatment of his/her ocular condition at that time. He/ She will receive the treatment required for his/ her eye condition as per established clinical guidelines.

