4.4.2 Data Collection and Follow-up for Withdrawn Subjects

If a subject withdraws from the study prior to 8 weeks, the subject will be asked to complete the procedures outlined in the 10 week visit as well as the Test Substance Tolerance scale from 8 weeks, as soon as possible. Subjects who voluntarily withdraw from the study between 8 weeks and 10 weeks will be asked to complete procedures outlined in the 10 weeks visit as soon as possible. Subjects who

are withdrawn due to adverse events will be followed at least until resolution or stabilization of the adverse event.

If the subject remains in the study for safety evaluation, follow-up visits will be scheduled according to the schedule of visits and procedures found in the synopsis.

5 Study Drug

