6.5.6 Visit 6: Week 8 (± 2 days)

Treatment Visit (after any dose for that day)

- Vital Signs
- OSDI
- Fluorescein and Lissamine Dye staining, and Schirmer 1 test
- Keratograph Oculus Redness Score
 - > Non-invasive Keratography Tear Film Break-up Time (NIKBUT)
 - > Tear Meniscus Height (TMH)
- TearLab Osmolarity Test
- InflammaDry Test for MMP-9 Protein
- Clinical Global Impression, Subject Global Assessment
- Test Substance Tolerance (VAS)
- Ophthalmic Examination (slit lamp examination, Ocular surface redness score)
- Tear fluid collection for analysis (PicoGreen, Cellometry)
- Physical Inspection of the Nose and Oropharynx
- Conjunctival and eyelid margin cultures
- Review the subject's diary and record changes in concomitant medication, deviations from drug schedule and adverse events.

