6.5.7 Visit 7: Week 10 (± 2 days)

Follow-Up Visit

- Vital Signs
- BSCVA (Snellen's chart)
- OSDI
- Clinical Global Impression, Subject Global Assessment
- Ophthalmic Examination (slit lamp examination, Ocular surface redness score)
- Physical Inspection of the Nose and Oropharynx
- Record changes in concomitant medication and adverse events.

7 Statistical Plan

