7.1 Sample Size Determination

The sample size is based on the primary efficacy end point (corneal RBS score) using the following assumptions: (i) mean RBS score in ocular GVHD population = 3.1, (ii) sigma (standard deviation) = 2.5, (iii) expected mean based on 60% effect = 1.24. These assumptions are based on our preliminary data in ocular GVHD patients where we found that treatment with DNase I eye drops reduced RBS score by 80% (mean).²⁵ A total of 30 subjects in each group will be required to detect the difference between groups using a 2-sided two-sample t test with an alpha level of 0.05 and 80% power. We elected to enroll 36 subjects per group.

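### Subjects withdrawn before week 8 for stopping drug or resuming lenses have no dye staining at exit, so no post-baseline primary score is secured for them, despite the intent-to-treat statement

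*Combined protocol and SAP*

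**What the plan says.** **Withdrawal rule.** Section 5.7 (Rescue Plan) reads: "If contact lens wear is reinstituted and/or the study drug is discontinued, the subject will be withdrawn from the study". Section 5.6 repeats it for clinical worsening: if "the study drug is withdrawn, the subject will be withdrawn from the study". Stopping drug is one of three listed responses to worsening or adverse events. The other two (more artificial tears, more Restasis or corticosteroids) keep the subject in the study.

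**Exit assessments.** Under section 4.4.2, when a subject leaves before week 8, "the subject will be asked to complete the procedures outlined in the 10 week visit", together with the week-8 tolerance scale. The ophthalmic item in the week-10 list (6.5.7) is "Ophthalmic Examination (slit lamp examination, Ocular surface redness score"; staining is not listed there. Section 4.4.2 adds a conditional route: "If the subject remains in the study for safety evaluation, follow-up visits will be scheduled" according to the normal schedule.

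**Where staining is done.** The Schedule of Visits and Procedures marks it at screening, Day 1 pre-dose and week 8 only. The week-8 list (6.5.6) includes "Fluorescein and Lissamine Dye staining, and Schirmer 1 test". Section 3.2 makes corneal staining after 8 weeks the primary efficacy endpoint.

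**Analysis.** Section 7.2 commits to intent-to-treat, with multiple imputation when less than 25% is missing. It gives no imputation model. Section 7.3 limits the analysis population to subjects with at least two weeks of treatment and a week-2 visit.

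**The concern.** An intent-to-treat comparison needs the week-8 staining score, or a credible substitute, from every randomised subject. Here the protocol itself creates part of the gap. It withdraws subjects for stopping drug, asks them back for an exit visit, and leaves the primary measurement off that visit.

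Because stopping drug is a response to worsening or adverse events, the eyes without a score may be those that did worst, so missingness may depend on outcome. More such losses on vehicle would shrink the observed difference; more on drug would enlarge it. Imputation corrects this only as far as the other recorded data predict the missing score.

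Section 7.3 adds a second departure from intent-to-treat. It removes randomised subjects on the basis of what happened after randomisation, including very early stopping.

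**Working it through.** **1. Trace an early leaver through the text.** A subject stops drug at week 5, say. Sections 5.6 and 5.7 withdraw the subject, and 4.4.2 calls for the week-10 list plus the tolerance scale. Staining scores on file are screening and Day 1. Post-baseline staining scores required: none. A subject who leaves after week 8 already has the score and is unaffected.

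**2. Reproduce the plan's sample size.** Section 7.1 gives means of 3.1 and 1.24 (difference 3.1 − 1.24 = 1.86), SD 2.5, two-sided alpha 0.05 and 80% power. An exact two-sample t test (noncentral t, noncentrality 1.86 / (2.5 × √(2/n))) gives power 79.5% at n = 29 and 80.9% at n = 30. The stated 30 per group reproduces. At the 36 enrolled, power is 87.6%.

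These inputs are for the RBS score: "The sample size is based on the primary efficacy end point (corneal RBS score". The current endpoint is a fluorescein score over 5 zones graded 0–3, for which no SD or expected difference is given. Steps 3 and 4 are therefore on the RBS scale and only illustrate size.

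**3. Possible bias.** Assumptions, since the documents give none: k of 36 are lost from one arm only, and their mean is e = 2.5 (1 SD) worse than that arm's full mean. The observed arm mean is then too low by k/(36 − k) × e. The second shift column assumes imputation recovers half of the excess.

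| k lost | Shift, nothing recovered | 1.86 becomes (lost on vehicle / on drug) | Shift, half recovered | 1.86 becomes (vehicle / drug) |
|---|---|---|---|---|
| 2 | 2/34 × 2.5 = 0.147 | 1.71 / 2.01 | 0.074 | 1.79 / 1.93 |
| 4 | 4/32 × 2.5 = 0.312 | 1.55 / 2.17 | 0.156 | 1.70 / 2.02 |
| 6 | 6/30 × 2.5 = 0.500 | 1.36 / 2.36 | 0.250 | 1.61 / 2.11 |

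If the arms lose 6 and 2, the unrecovered shift is 0.500 − 0.147 = 0.353.

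**4. Power cost of keeping off-drug scores.** Let p be the share discontinuing, and suppose drug-arm stoppers keep no benefit. The difference becomes 1.86 × (1 − p) at n = 36. Mixing stoppers and non-stoppers adds p(1 − p) × 1.86² to the drug-arm variance, which gives the lower figure of each pair. The comparison column loses the same share from both arms: n = 36 × (1 − p), difference 1.86.

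| p | Difference kept | Power, scores kept (mixture variance – SD 2.5) | n per arm, scores lost | Power, scores lost | n per arm for 80% with scores kept (SD 2.5 – mixture variance) |
|---|---|---|---|---|---|
| 5% | 1.767 | 83.6–84.1% | 34.2 | 85.8% | 33 |
| 10% | 1.674 | 79.0–80.0% | 32.4 | 83.9% | 36–37 |
| 15% | 1.581 | 73.9–75.4% | 30.6 | 81.7% | 41–42 |
| 20% | 1.488 | 68.3–70.2% | 28.8 | 79.2% | 46–48 |

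If stoppers keep half the benefit (difference 1.86 × (1 − p/2), SD 2.5), power is 85.9%, 84.1%, 82.1% and 80.0%, about the same as losing them. The scores-lost column assumes that the losses are unrelated to outcome, which is the point in doubt.

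**The case against.** **Withdrawal does not end contact.** A reader might infer that these subjects disappear. They do not. Section 5.6 plans weekly follow-up after worsening until symptoms resolve. Section 4.4.2 follows adverse-event withdrawals to resolution or stabilisation and keeps those who stay for safety evaluation on the normal schedule, which includes week-8 staining. This stands, and it narrows the point to a missing guarantee: none of these routes requires staining at an early exit or assures a week-8 score.

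**A later score would not be discarded.** A reader might also infer that a week-8 score taken after withdrawal is barred from the efficacy analysis. No text excludes it. For a subject who meets section 7.3, the intent-to-treat rule in 7.2 would by default place it in the randomised arm.

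**Imputation has useful predictors.** Besides baseline staining, OSDI, CGI, SGA and redness, the slit-lamp examination at every visit records superficial punctate keratopathy and corneal filaments (3.4.2). Week-4 tear break-up time, meniscus height, osmolarity and MMP-9 exist for those who got that far. Recovering nothing is therefore an extreme case. Still, none of these is the 5-zone score, and no imputation model is specified.

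**Few may leave, and imbalance would show.** Section 5.6 expects no significant worsening. The primary safety endpoint (3.4) is the proportion completing eight weeks, so unequal stopping would be reported beside the efficacy result. Both are fair. Reporting an imbalance reveals the problem but does not supply the scores.

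**Lens-resumers gain little.** Section 5.6 says "Contact lenses can directly reduce corneal SPK and staining", so a week-8 score taken in lenses is not usable as it stands and would be imputed either way. This is partly a choice of what to estimate. For this group the gain is one exit staining taken before lenses restart.

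**Conclusion.** The point holds as a gap in data collection. For subjects withdrawn before week 8 under sections 5.6 and 5.7, the required procedures secure no post-baseline primary score. Separately, section 7.3 contradicts the intent-to-treat statement in 7.2. Both are read directly from the text and rest on no assumption.

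The consequence is less certain. The documents give no discontinuation rate and no severity for those who stop, so neither the number affected nor the direction of bias can be derived. A reader might infer that the treatment estimate will be biased, or biased in favour of drug; the documents support neither. The shifts of 0.15 to 0.50 on a difference of 1.86 assume one-sided loss, leavers 1 SD worse, RBS inputs and no recovery by imputation. Half recovery halves them.

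Nor should one infer that 36 per arm safely covers 10% discontinuation once off-drug scores are kept. If drug-arm stoppers keep no benefit, power there is 79–80%, and 37 per arm are needed when the mixture variance is counted.

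The change is worth making because a score not taken cannot be recovered later and the remedy is cheap.

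**What to change.** 1. **Section 4.4.2:** add corneal and conjunctival staining to the early-exit list, done before lens wear restarts where possible. Use it as a predictor in the multiple imputation, not as the week-8 value.
2. **Sections 5.6 and 5.7:** state that stopping study drug ends treatment only. Ask willing subjects to attend for week-8 staining and analyse that score as randomised. Rescue decisions stay with the investigator.
3. **Section 7.3:** define the primary efficacy set as all randomised subjects, with week 8 imputed where it is missing or was taken after lens wear resumed. Say openly that this treats lens-resumers differently from drug-stoppers who stay off lenses.

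**Cost.** Protocol and SAP wording, a few minutes of staining by existing staff at a visit already requested, and a small burden on subjects off drug. Some will decline and some will resume lenses, so not every score will be recovered. The main downside is dilution. If drug-arm stoppers keep no benefit, power falls by about 2, 4–5 and 9–11 points at 5%, 10% and 20% discontinuation, compared with losing the same share from both arms. There is almost no fall if they keep half. No extra enrolment is proposed for this preliminary-efficacy trial.
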